# **5.2.** Treatment Groups

This is a Phase 2, multicenter, open-label study. For the purpose of analysis, the 20 mg once weekly dosing period in Group A and the 2.5 mg QD dosing period in Group B are considered maintenance dosing periods. Data will be presented in summary tables by actual received treatment regimen and combined, with an exception for participants who cross over to the selected treatment regimen after the start of the maintenance dosing period. There will not be any statistical comparison between the treatment groups.

For participants who cross over from the initially assigned treatment regimen to the selected treatment regimen, if the crossover happens on/before the start of the maintenance period, then the participant will be summarized, according to the actual received treatment, in the selected treatment regimen; otherwise, the participant will be summarized in:

- A separate treatment regimen (ie, Crossover) for the safety summaries during the maintenance dosing period (eg. summaries of TEAEs and exposure).
- The initially assigned treatment regimen for all other summaries.

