## 6.4. Exposure

For participants in the safety population, exposure to INCB050465 will be summarized descriptively as the following:

• **Duration of treatment (days)**: Date of last dose – date of first dose + 1.

- **Duration of treatment during the initial QD dosing period (days)**: Date of last dose during initial QD dosing period date of first dose + 1.
- Duration of treatment during the maintenance dosing period (days): Date of last dose date of first dose during the maintenance dosing period + 1. Crossover participants who switched to the selected treatment regimen after the start of the maintenance dosing period will be summarized in a separate group (ie, Crossover).
- Average reported daily dose during the initial QD dosing period (mg/day): Total reported dose taken during initial QD dosing period (mg) / duration of treatment during the initial QD dosing period (days).
- Average reported daily dose during the maintenance dosing period (mg/day): Total reported dose taken during the maintenance dosing period (mg) / duration of treatment during the maintenance dosing period (days). Crossover participants who switched to the selected treatment regimen after the start of the maintenance dosing period will be summarized in a separate group (ie, Crossover).
- **Dose modifications:** Number of participants who had dose reduction and interruption will be summarized. The number of dose reductions and the number of interruptions for each participant will be summarized.

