#### 9.2.3. Adverse Event Summaries

Overall summaries of TEAEs by treatment regimen will be provided during the INCB050465 initial QD dosing period, maintenance dosing period, and overall period (ie. all TEAEs regardless of the timing of occurrence). These summaries will include the following:

- Number (%) of participants reporting any TEAEs
- Number (%) of participants reporting any Grade 3 or higher TEAEs
- Number (%) of participants reporting any serious TEAEs
- Number (%) of participants reporting any TEAEs related to INCB050465
- Number (%) of participants reporting any Grade 3 or higher TEAEs related to INCB050465
- Number (%) of participants reporting any serious TEAEs related to INCB050465

- Number (%) of participants who had TEAE with fatal outcome
- Number (%) of participants with INCB050465 dose reductions because of TEAEs
- Number (%) of participants who temporarily interrupted INCB050465 because of TEAEs
- Number (%) of participants who permanently discontinued INCB050465 because of TEAEs

The following summaries will be produced for TEAEs during the overall period by MedDRA term (if 10 or fewer participants appear in a table, a listing may be appropriate):

- Summary of TEAEs by SOC and PT
- Summary of TEAEs by PT in decreasing order of frequency
- Summary of TEAEs by SOC, PT, and maximum severity
- Summary of TEAEs by PT and maximum severity in decreasing order of frequency
- Summary of Grade 3 or higher TEAEs by SOC and PT
- Summary of Grade 3 or higher TEAEs by PT in decreasing order of frequency
- Summary of serious TEAEs by SOC and PT
- Summary of serious TEAEs by PT in decreasing order of frequency
- Summary of INCB050465 treatment-related TEAEs by SOC and PT
- Summary of INCB050465 treatment-related TEAEs by PT in decreasing order of frequency
- Summary of INCB050465 treatment-related TEAEs by SOC, PT, and maximum severity
- Summary of Grade 3 or higher INCB050465 treatment-related TEAEs by SOC and PT
- Summary of INCB050465 treatment-related serious TEAEs by SOC and PT
- Summary of TEAEs with a fatal outcome by SOC and PT
- Summary of TEAEs leading to INCB050465 dose reduction by SOC and PT
- Summary of TEAEs leading to INCB050465 dose interruption by SOC and PT
- Summary of TEAEs leading to discontinuation of INCB050465 by SOC and PT
- Summary of selected TEAEs of special interest by maximum severity
- Summary of time to onset of selected TEAEs of special interest

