- Summary of time to onset of selected TEAEs of special interest: life-table method
- Summary of longest duration of selected TEAEs of special interest

The following supporting summaries will be produced for TEAEs during the INCB050465 initial QD dosing period and the maintenance dosing period by MedDRA term. For the supporting summaries during the maintenance dosing period, participants who cross over to the selected treatment regimen after the start of the maintenance dosing period will be summarized in a separate group (ie, Crossover).

- Summary of TEAEs by PT in decreasing order of frequency
- Summary of TEAEs by PT and maximum severity in decreasing order of frequency
- Summary of Grade 3 or higher TEAEs by PT in decreasing order of frequency
- Summary of serious TEAEs by PT in descending order of frequency
- Summary of TEAEs with a fatal outcome by SOC and PT
- Summary of TEAEs leading to discontinuation of INCB050465 by SOC and PT

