- Section 9.2.2 was updated to include details of analyses on time to onset of selected TEAEs of special interest. Summaries of longest duration of selected TEAEs of special interest were added to have a better understanding of the safety profile in terms of duration of class-effect AEs as well as AEs influenced by treatment regimens. "Grade 2 or higher" was changed to "Grade 3 or higher" for time to onset summary of rash. This change was made to be consistent with other PI3K inhibitors, which highlighted more severe cutaneous reactions graded as Grade 3 or higher in the labeling. "Herpes simplex virus infection" was changed to "herpes simplex" based on the MedDRA coding dictionary as a broader term. Exfoliative dermatitis was added to the list of TEAEs of special interest.

- Section 9.2.3 was updated to include summary of TEAEs by PT and maximum severity in decreasing order of frequency, summary of longest duration of selected TEAEs of special interest, and additional supporting summaries during the INCB050465 initial QD dosing period and the maintenance dosing period, which will provide supportive data of the safety profile of the maintenance dose. Summary of nonserious TEAEs by SOC and PT was removed because it will not be used for the clinical study report but will be provided for result disclosure.
- Section 9.3.2 was modified to include ALT and AST in the line graphs as additional supportive analyses for laboratory events of special interest.
- Section 9.3.3 was added to identify potential Hy's law events to better monitor liver toxicity.
- Section 9.3.4 was updated to align with the analysis plan for adverse events of special interest. Summary of worsening of laboratory events of special interest was removed because this is covered by the summary of worsening of laboratory abnormalities.
- Section 9.5 was updated to change the high threshold of QTcF and QTcB interval from 460 to 450 milliseconds for purpose of analysis. This change is to comply with the categories outlined in FDA Guidance for Industry (E14 Clinical Evaluation of QT/QTc Interval Prolongation and Proarrhythmic Potential for Non-Antiarrhythmic Drugs) used to characterize outliers in OTc values.

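### Maintenance-period safety tables move late switchers wholly into Crossover, so the remaining Group A column is a selected group whose AE-discontinuation figures are expected to run somewhat high

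*SAP*

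**What the plan says.** SAP 5.2 sets two rules for a participant who crosses over after the maintenance period has started. For maintenance-period safety the participant goes into "A separate treatment regimen (ie, Crossover) for the safety summaries during the maintenance dosing period". For everything else the participant stays in "The initially assigned treatment regimen for all other summaries". A participant who switches on or before the start of maintenance is counted in the selected regimen and is not at issue here.

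SAP 6.4 measures maintenance exposure as last dose minus "date of first dose during the maintenance dosing period + 1", and adds that "Crossover participants who switched to the selected treatment regimen after the start of the maintenance dosing period will be summarized in a separate group". SAP 9.2.3 says the same of the maintenance-period TEAE tables, where "participants who cross over to the selected treatment regimen after the start of the maintenance dosing period will be summarized in a separate group". Those tables include TEAEs leading to discontinuation, and the overall TEAE summary, also given by dosing period, includes "Number (%) of participants who permanently discontinued INCB050465 because of TEAEs".

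Three other statements matter:
- The SAP Amendment 1 log records that Group B (2.5 mg daily) was selected.
- SAP 3 and Protocol 4.1 let participants on the non-selected regimen switch only if they have not met study-treatment withdrawal criteria. Protocol 5.5.1 lists unacceptable toxicity among those criteria.
- SAP 7.4.2 and 7.4.3 plan DOR and PFS sensitivity analyses that drop assessments after crossover and censor there. No counterpart is planned for maintenance-period safety.

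**The concern.** The rule reassigns people, not person-time. It sorts them by an event that happens after maintenance begins and requires still being on treatment. Someone in Group A who stops early for an adverse event can never leave the Group A column. Someone who stays on long enough can.

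Two distortions follow in the Group A column, even if the two regimens are identical. AE discontinuation should look too frequent, because early stoppers are over-represented. Events that build up with time on drug should look too rare as crude percentages, because the people with long exposure have gone.

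The Crossover column holds both regimens, and the planned average daily dose will not reveal the mix. Full weekly dosing is 20/7 = 2.86 mg/day and full daily dosing is 2.50 mg/day.

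Protocol 1.4 proposes both maintenance regimens as ways to reduce AEs leading to withdrawal, so a tilted AE-discontinuation figure for the weekly regimen touches an outcome the design cares about.

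**Working it through.** The plan gives no figure on this point to reproduce. It gives no number of switchers, no switch times and no Group A AE-stop rate. The only sourced input is the size of Group A: about 25, half of the first 50 (Protocol 4.1). Everything else below is assumed, and the two regimens are taken as identical, so any shift is an artefact of the column definition.

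**Constant-hazard check.** Monthly hazards are 0.03 for an AE stop and 0.04 for any other stop (0.07 in total), over 18 months of maintenance. The switch is offered at a uniform time in months 0–10, and a share s of those still on treatment accept.

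- AE stops with nobody switching: (0.03/0.07) × (1 − e^−1.26) = 0.4286 × 0.7164 = 30.7%.
- Mean maintenance time: 0.7164/0.07 = 10.23 months.
- On treatment at the offer, on average: P = (1 − e^−0.7)/0.7 = 0.719.
- AE stops after the offer: 0.4286 × (0.719 − 0.2837) = 0.1866.
- Months after the offer: (0.719 − 0.2837)/0.07 = 6.22. Months before it among those still on treatment: 3.18. Sum: 9.40.

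Remaining Group A then has:
- crude AE discontinuation = (0.3070 − 0.1866s)/(1 − 0.719s)
- rate = (0.3070 − 0.1866s)/(10.23 − 9.40s)

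Splitting at the switch keeps the same AE stops but also keeps pre-switch time:
- rate = (0.3070 − 0.1866s)/(10.23 − 6.22s)

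| Uptake s | Remaining A, n of 25 | Crude AE stop (30.7% if none switch) | Shift in patients | Rate per 100 person-months (true 3.0) | Rate after split |
|---|---|---|---|---|---|
| 25% | 20.5 | 31.7% | 0.2 | 3.3 | 3.0 |
| 50% | 16.0 | 33.4% | 0.4 | 3.9 | 3.0 |
| 75% | 11.5 | 36.3% | 0.6 | 5.2 | 3.0 |

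The patient shift is n times the difference in percentages; at 75%, 11.5 × (0.363 − 0.307) = 0.6. In simulated trials of this size at 75% uptake, the crude percentage has a 95% range of 9–67%.

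**Timing of the offer.** With the offer at months 6–16, P = (e^−0.42 − e^−1.12)/0.7 = 0.4725. At 75% uptake n = 25 × (1 − 0.75 × 0.4725) = 16.1 and crude AE discontinuation is 38.2%, a shift of 16.1 × (0.382 − 0.307) = 1.2 patients.

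**Time-accruing event** (assumed monthly hazard 0.10, simulated, offer at 0–10 months). The crude percentage with no switching is 56.0%. Remaining Group A shows 49.0% at 50% uptake and 41.4% at 75%. The rate per person-month is about the same in every column, so this distortion comes from shorter exposure alone.

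**Crossover column.** Across the simulated settings, weekly dosing makes up 17–65% of its time. Full dosing would then average 2.50 + 0.357 × share, or 2.56–2.73 mg/day.

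**Two-stage check, which does not assume constant risk.** Let e be the share stopping for an AE before the switch, o the share stopping for other reasons, and L the later AE-stop risk.
- Remaining A = [e + (1−e−o)(1−s)L]/[1 − (1−e−o)s].
- With no switching it is e + (1−e−o)L.
- Take e = 19%, o = 20%, L = 10%, s = 50%. The 19% is borrowed only as an illustration from the earlier study's 12 of 63 in Protocol 1.3. The result is 0.2205/0.695 = 31.7% against 25.1%: 17.4 patients × 6.6 points = 1.1 patients.
- At s = 75% it is 37.8%: 13.6 × 12.7 points = 1.7 patients.
- With e = 35% (the earlier study's 7 of 20 responders, Protocol 1.4) and s = 75% it is 54.5% against 39.5%: 16.6 × 15.0 points = 2.5 patients.
- The figure is too high exactly when L < e/(e+o). With e = 10%, o = 20% and L = 35% it reverses slightly: 33.3–34.4% against 34.5%.

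**What a split does to crude percentages** (offer at 0–10 months). Keeping switchers in Group A but cutting them at the switch gives AE discontinuation of 0.3070 − 0.1866s, which is 21.4% at 50% uptake and 16.7% at 75%. Both are further from 30.7% than the current plan's 33.4% and 36.3%.

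**The case against.** The case for leaving the plan alone is substantial, and most of it stands.

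- The planned outputs are n (%), not rates. On that scale the shift is a fraction of a patient in the constant-hazard table above and mostly small elsewhere. This stands, and it is why the point is minor.
- A split on its own would make the planned percentages worse. This also stands and limits the remedy.
- The Amendment 1 log says the added tables are ones "which will provide supportive data of the safety profile of the maintenance dose". Because that log also names 2.5 mg daily as the selected maintenance dose, the phrase most naturally means the selected regimen. Keeping late switchers out of the Group B column protects that profile.
- The tables are described as supporting, no between-group comparison is planned (SAP 3.2), maintenance duration is shown by column (Table 3.1.3), and AE and dosing listings are planned.
- Protocol 5.4.1.4 says most immune-related events come after the first 9 weeks. A date cut can therefore credit a late effect of weekly dosing to the period after the switch. This is a real cost of the fix.

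What the objection does not remove is that the Group A maintenance column, read as a description of the weekly regimen, is selected. The overall-period tables are not a substitute: they keep late switchers in Group A but mix in events on daily dosing.

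A reader might infer that the selected-dose safety profile or the efficacy results are biased by this rule. The documents do not support that. Late switchers are not placed in the Group B maintenance column, and the combined column contains everyone. The rule is confined to maintenance-period safety and exposure. The main ORR and CRR, the futility rule, and the initial-QD and overall-period tables follow the assigned regimen for late switchers or pool the groups.

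**Conclusion.** The point holds as a minor one. The text moves the whole late switcher into Crossover, and the eligibility condition for switching makes the remaining Group A column selected. That much follows from the documents alone.

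The direction (AE discontinuation too high, time-accruing events too low as crude percentages) is expected but not certain. It depends on later AE-stop risk not being high relative to the AE share of early stops, and on switching not being strongly tied to tolerability.

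The size rests wholly on assumed uptake, timing and hazards. Crude AE discontinuation moves by less than one patient under constant hazards with an offer in the first 10 months. It moves by 1.2 patients with a late offer and 75% uptake, and by more (2.5 in the largest case shown) if AE stops are concentrated before the switch. With about 25 people in Group A, all of these are smaller than sampling error. If few switched, the effect nearly vanishes.

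**What to change.** Keep the planned n (%) maintenance tables. Add a footnote that the remaining Group A and Crossover columns are defined by a post-baseline event.

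Add one supplementary maintenance-period analysis that divides exposure and TEAEs at the crossover date. Time and events before the switch go under the initially assigned regimen; those after it go under Crossover. Report it only as exposure-adjusted incidence rates or as time-to-event estimates censored at crossover. Do not report crude percentages on the split data, which would be biased low.

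The cost is a sentence each in SAP 5.2, 6.4 and 9.2.3, a date split in programming, and one added output. No new data are needed, because SAP 7.4.2 and 7.4.3 already use the time of crossover.

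There are three downsides:
- Switchers appear in two columns.
- Late effects of weekly dosing may be counted after the switch.
- Censoring at the switch may be informative. In an assumed case where half the participants have three times the AE-stop hazard and uptake varies with risk between 30% and 90%, the split rate is 2.6–3.2 per 100 person-months against a true 2.8. The remaining Group A column gives 3.3–5.4.

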#### 7.3.1. Best Overall Response and Overall Response Rate

For responses determined by the IRC, the best overall response for each participant will be provided by the Clinical Reviewer. A participant is considered an objective responder if they have a best overall response of CR or PR.

The ORR is the proportion of objective responders. Participants who do not have sufficient baseline or on-study response assessment information to be adequately assessed for response status will be included in the denominators in the calculation of ORR.

Best overall response as determined by the IRC will be descriptively summarized by treatment groups and combined. The ORR as determined by the IRC will be estimated with 95% CIs. Confidence intervals will be calculated based on the exact method for binomial distributions.

Because participants who switched to the selected treatment regimen after starting the maintenance dose received a mixture of the non-selected and selected maintenance regimens and could confound the efficacy evaluation of the non-selected treatment regimen, a sensitivity analysis of ORR as determined by IRC will be provided to summarize these crossover participants as a separate treatment regimen. In addition, the number of participants who achieved best overall response as determined by IRC after the time of crossover along with the best overall response data will be presented under this separate treatment regimen.

When applicable, sensitivity analysis of ORR as determined by the IRC may be provided excluding participants that do not have evaluable radiological images at baseline per the IRC.

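### Overall-period safety tables keep late switchers in the regimen they left, and no crossover-separated version is planned for special-interest events or laboratory data

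*SAP*

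**What the plan says.** SAP 5.2 tabulates by regimen actually received and combined, with a stated exception for participants who switch to the selected regimen. It has three branches:

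- Switch at or before the start of maintenance: "if the crossover happens on/before the start of the maintenance period, then the participant will be summarized, according to the actual received treatment", that is, under the selected regimen.
- Later switch, maintenance-period safety: "A separate treatment regimen (ie, Crossover) for the safety summaries during the maintenance dosing period (eg. summaries of TEAEs and exposure").
- Later switch, everything else: "The initially assigned treatment regimen for all other summaries".

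SAP 9.2.3 defines the "overall period (ie. all TEAEs regardless of the timing of occurrence"), and most adverse event tables belong to it: "The following summaries will be produced for TEAEs during the overall period by MedDRA term". That list contains the special-interest tables, for example "Summary of selected TEAEs of special interest by maximum severity". A shorter list of six supporting tables is repeated for the initial and maintenance periods. In the maintenance versions, those who switch "after the start of the maintenance dosing period will be summarized in a separate group (ie, Crossover").

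For efficacy, SAP 7.3.1 says that participants with mixed maintenance exposure "could confound the efficacy evaluation of the non-selected treatment regimen". SAP 7.3.1 and 7.4.1 to 7.4.3 therefore add crossover analyses for ORR, CRR, DOR and PFS. SAP 11.2 records that these came with Amendment 2, which was written to answer FDA comments.

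**The concern.** The two regimens are identical for 8 weeks and differ only afterwards, so differences between them in safety arise in maintenance. A participant who switches part-way through maintenance contributes experience on both maintenance doses. In the overall-period tables all of it goes to the regimen that was left.

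The SAP treats this mixture as a problem for efficacy and plans analyses for it, but plans nothing equivalent for overall-period safety. The gap is widest for the events of most interest with this class. Protocol 5.4.1.4 expects most immune-related events after the first 9 weeks of treatment. Protocol 1.3 reports that all but one of the events behind the 12 discontinuations for adverse events in the earlier study came after the 9-week assessment. The special-interest tables cover much of that ground, and they exist only in overall-period form.

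At stake is how far a reader can take the Group A column as a description of Group A's regimen. No formal comparison is planned, but columns printed side by side will be read side by side.

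**Working it through.** The plan attaches no figure to this rule, so there is none to reproduce. The check is a cross-reading, followed by simple arithmetic for scale.

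**Step 1: which column is affected.** SAP 11.2 (Amendment 1, note on Section 6.4) records that Group B, 2.5 mg once daily, was selected. Late switchers therefore move from A to B and stay in the Group A column.

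**Step 2: is there a cut at the switch?**

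- Treatment-emergent window (SAP 9.2.1): first dose to 30 days after the last study drug dose. No cut.
- Onset of special-interest events (SAP 9.2.2): event-free participants are censored at the earlier of 30 days after the last dose and the last study visit. No cut.
- Laboratory shifts (SAP 9.3.2): worst grade at any time after baseline. No cut.
- Onset of worsening laboratory events (SAP 9.3.4): censored at the last visit with a grade. No cut.
- Vital signs and ECGs (SAP 9.4, 9.5): no period split and no crossover rule; abnormality listings show the assigned regimen.

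**Step 3: what has a crossover-separated version?**

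- Separated: the maintenance-period overall summary (by the SAP 5.2 rule); maintenance exposure (SAP 6.4); and six supporting maintenance tables, namely preferred term, preferred term by maximum severity, Grade 3 or higher, serious, fatal, and leading to discontinuation.
- Not separated: special-interest events (maximum severity, time to onset, life-table, longest duration); treatment-related tables by term; dose reduction and interruption by term; laboratory, vital sign and ECG summaries.

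Even where Crossover is separated, the group holds whole participants for the whole maintenance period. It does not isolate what happened after the switch.

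**Step 4: scale.** Half of the first 50 participants gives 50/2 = 25 in Group A. One participant whose first event of a given type follows the switch adds 1/25 = 4 percentage points to that incidence. Anyone who switched at or before the start of maintenance leaves this denominator, which makes the step slightly larger.

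The documents give neither the number of late switchers nor any event rates after a switch, so a total needs assumptions. Let k be the number of late switchers, p the incidence before the switch, and q the risk of a first event afterwards among those still event-free. Compared with stopping the count at the switch:

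added incidence = (k/25) × (1 − p) × q

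- Low end, assuming k = 5, p = 40%, q = 10%: 0.20 × 0.60 × 0.10 = 1.2 points.
- High end, assuming k = 20, p = 20%, q = 30%: 0.80 × 0.80 × 0.30 = 19.2 points.

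Every input except 25 is assumed. The width of the range shows that the effect cannot be pinned down from the documents.

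**The case against.** The strongest reply is that the rule is disclosed and largely handled. SAP 5.2 announces the exception in the same sentence that sets the received-treatment basis. A reader might infer that the SAP contradicts its own principle. It does not: this is a declared departure, though no reason is given for applying it to safety.

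The maintenance-period tables also cover the time when the regimens differ. Colitis, diarrhea or pneumonitis reported as preferred terms will appear there by severity with Crossover apart, and listings of adverse events and drug administration are planned. That stands for general events. It does not supply special-interest onset or duration, or any laboratory table.

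A reader might also infer that both regimens' results are distorted. The selected column gains no mixed-exposure participants; it only lacks the switchers' later experience. The combined column is unchanged.

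Nor do the documents show that late toxicities fall mainly after a switch, or that events after a switch were caused by the selected regimen. The protocol times immune-related events from the start of treatment, switch times are not given, and earlier dosing may contribute to a later event. A separate group avoids the question because it credits neither regimen.

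Finally, visit summaries of laboratory, vital sign and ECG data at maintenance visits could be argued to fall under the maintenance-period branch. SAP 9.3 to 9.5 do not say so, and worst-grade shifts and time to onset span both periods in any case.

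**Conclusion.** The point holds in a limited form. The Group A column of the overall-period adverse event, special-interest and laboratory tables will include events that arose after participants had left that regimen. For special-interest events and laboratory data, no planned table lets a reader see the result with those participants apart.

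The effect is about 4 points of Group A incidence per affected participant, given a group of about 25. The total is unknown. A statement such as a 12-point shift (3/25) would rest on an assumed count of three participants that has no source in the documents. If nobody switched late, the effect is nil.

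The study is descriptive, general events are partly covered, and the selected and combined columns gain no mixed or misplaced events. Severity is therefore minor to moderate: an omission worth closing because the SAP already uses the remedy for efficacy.

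**What to change.** Keep the planned tables and add to them, in SAP 5.2, 9.2.2, 9.2.3, 9.3 and Appendix A:

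- Supplementary versions of the overall-period adverse event, special-interest and laboratory tables, showing late switchers as a separate participant-level group with its own denominator, as Table 2.4.1 does for response.
- A sensitivity analysis of time to onset for special-interest and worsening laboratory events, censored at the switch, on the pattern already set for DOR and PFS.
- The number of late switchers and their switch times, so that readers can judge the scale.

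Leave the combined column as it is. For vital signs and ECGs, a sentence in SAP 5.2 confirming the column used is probably enough.

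Splitting each switcher's events between columns in the main tables is not advised. It would clash with the existing Crossover group, which is defined by participant, and would put one person in two columns without a denominator rule.

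The cost is extra programming and more output. The assigned-regimen group becomes smaller in the supplementary tables. Censoring at the switch may be informative if the decision to switch was related to tolerability, so that analysis should be labelled as sensitivity only.
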